2.4.3 Multiple assessments within visit windows

When there are *multiple assessments* in a particular visit window, the following rules are applied to select one value “representing” the subject in summary statistics in a visit window (See [Table 2-1](#)).

For baseline assessment definition see [Section 2.1.4](#). For post-baseline visit windows the following applies (unless otherwise specified):

- for *quantitative variables*, the *closest* to the actual visit is chosen (if two assessments have the same distance, then the earlier one will be chosen);
- for *qualitative variables*, the *worst* record is selected. It is noted that in the analyses performed, *worst* case is always well defined (e.g., for urine protein values “+” and “++”, the worst case is defined as “++”),
- in case qualitative variables are based on quantitative variables, e.g. PASI 90 response, the visit will be assigned to the quantitative variable, and this visit will be used for the derived qualitative variable.

Table 2-2 Rules for selecting values for analysis within a given visit window

Timing of measurement	Type of data	Rule
Baseline	All data	See Section 2.1.4
Post-baseline efficacy	All data [REDACTED] e.g., PASI, IGA	The measurement closest to the target day will be used. In the event two measurements are taken equally apart (e.g., 1 day before target date and 1 day after), the earlier one will be used. If two measurement are taken on the same day then select the first one using eCRF visit number. If two measurement have been taken on the same day and same visit then select the worst.
[REDACTED]	[REDACTED]	[REDACTED]
Post-baseline safety	Summary visit information (e.g. laboratory values, vital signs, etc.)	The (non-missing) measurement closest to the target day will be used. In the event two measurements are taken equally apart (e.g., 1 day before target date and 1 day after), the earlier one will be used. If two measurements are taken on the same day then select the first one (using the time). If two measurements are taken on the same date then use the first eCRF visit number (assuming this is the planned visit). If two measurements are taken on the same date/eCRF visit number then take the average value of these two results.
Post-baseline safety	Notable abnormalities (e.g. vitals signs) and CTCAE grades for laboratory values	The most extreme measurement in the window will be used. Note this means a subject can have a notably high and notably low measurement within an analysis period.

2.4.4 Prior, concomitant and post therapies

Medications will be identified using Novartis Drug and Therapy Dictionary (NovDTD) including Anatomical Therapeutic Chemical (ATC) code. Prior and concomitant treatments will be summarized by treatment group for the safety set unless otherwise specified. Concomitant treatments will be displayed for the treatment period.

Prior and concomitant medications will be summarized by treatment group in separate tables. Medications will be presented in alphabetical order, by ATC codes and grouped by *anatomical main group* (the 1st level of the ATC codes). Tables will also show the overall number and percentage of subjects receiving at least one drug of a particular ATC code and at least one drug in a particular anatomical main group.

Prior medications are defined as drugs taken and stopped prior to the first dose of study treatment. Any medication given at least once between the day of first dose of randomized study treatment, and last dose plus 84 days or last study visit (including follow-up visits) whichever occurs earlier will be a **concomitant** medication, including those which were started pre-baseline and continued into the treatment period.

Psoriasis specific summaries of prior and/or concomitant medication will be presented as in [Table 2-3](#), but as well for topical, phototherapy and photochemotherapy (yes/no) using the randomized set.

In addition, medical procedures and significant non-drug therapies as coded in MedDRA will be summarized.

Prior or concomitant medication will be identified based on recorded or imputed start and end dates of medication taken. Further rules will be given in [Section 5](#).

Table 2-3 Summary of previous psoriasis therapy

Level 1 description	Level 1 outcome	Level 2 description	Level 2 outcome	
previous therapy	yes/no			
systemic	No			
	Yes	number	1	
			2	
			>=3	
		failure*	no	
yes				
biologic	No			
	Yes	failure*	no	
			yes	
		type of previous biologic		
		anti-p40	no	
			yes	
		anti-TNF	no	
yes				
non-biologic systemic	No			
	Yes	failure*	no	
			yes	
		failure* to at least 2	no	
yes				

*: at least one therapy with lack of primary efficacy or lack of secondary efficacy or lack of tolerability

[figure not shown]
2.5 Analysis of the primary objective

The study objectives are defined as in study protocol [Section 2.1](#).

Treatment arms defined for efficacy analysis:

- Primary and secondary endpoint of PASI 90 and IGA 0/1 response at Week 16:
 - AIN457 300mg Q2W

- AIN457 300mg Q4W

2.5.1 Primary endpoint

The primary endpoint is PASI 90 response at week 16. The analysis of primary variable will be based on FAS.

2.5.2 Definition of PASI and related variables

The investigator or trained qualified designee will complete the PASI assessments. Whenever possible, the same evaluator should perform this assessment at all visits.

The total BSA affected by plaque-type psoriasis will be estimated from the percentages of areas affected, including head, trunk, upper limbs and lower limbs (see below for PASI assessment). The following calculations will be done: each reported percentage will be multiplied by its respective body region corresponding factor (head = 0.1, trunk = 0.3, upper limbs = 0.2, lower limbs = 0.4). The resulting 4 percentages will be added up to estimate the total BSA affected by plaque-type psoriasis. The PASI scoring system is further described in [Table 2-4](#).

A PASI score ([Fredriksson and Pettersson 1978](#), [Weisman et al 2003](#), [Gottlieb et al 2005](#)) will be derived as indicated in [Table 2-4](#). The head, trunk, upper limbs and lower limbs are assessed separately for erythema, thickening (plaque elevation, induration), and scaling (desquamation). The average degree of severity of each sign in each of the four body regions is assigned a score of 0-4. The area covered by lesions on each body region is estimated as a percentage of the total area of that particular body region. Further practical details help the assessment:

1. The neck is assessed as part of the head.
2. The axillae and groin are assessed as part of the trunk.
3. The buttocks are assessed as part of the lower limbs.
4. When scoring the severity of erythema, scales should not be removed.

Because the head and neck, upper limbs, trunk and lower limbs correspond to approximately 10%, 20%, 30% and 40% of the body surface area, respectively, the PASI score will be calculated using the formula:

$$\text{PASI} = 0.1 (E_h + I_h + D_h)A_h + 0.2 (E_u + I_u + D_u)A_u + 0.3 (E_t + I_t + D_t)A_t + 0.4 (E_l + I_l + D_l)A_l$$

where E, I, D, and A denote erythema, induration, desquamation, and area, respectively, and h, u, t, and l denote head, upper extremities, trunk, and lower extremities, respectively (see [Table 2-4](#)).

PASI scores can range from a lower value of 0, corresponding to no signs of psoriasis, up to a theoretic maximum of 72.0.

The investigator is responsible for collecting the components or scoring signs and total regional area for all visits. PASI and total BSA calculations will be calculated by clinform and will be used in the analysis and for derivation of PASI response values (see below).

Table 2-4 The PASI scoring system

Body region	Erythema (E)	Thickening (plaque elevation, induration, I)	Scaling (desquamation, D)	Area score (based on true area %, A)*
Head (H) [†]	0=none	0=none	0=none	0 = no involvement
	1=slight	1=slight	1=slight	1 = >0-<10%
	2=moderate	2=moderate	2=moderate	2 = 10-<30%
	3=severe	3=severe	3=severe	3 = 30-<50%
	4=very severe	4=very severe	4=very severe	4 = 50-<70%
Trunk (T) [‡]				5 = 70-<90%
				6 = 90-100%
	0=none	0=none	0=none	0 = no involvement
	1=slight	1=slight	1=slight	1 = >0-<10%
	2=moderate	2=moderate	2=moderate	2 = 10-<30%
	3=severe	3=severe	3=severe	3 = 30-<50%
Upper limbs (U)	4=very severe	4=very severe	4=very severe	4 = 50-<70%
				5 = 70-<90%
				6 = 90-100%
	0=none	0=none	0=none	0 = no involvement
	1=slight	1=slight	1=slight	1 = >0-<10%
Lower limbs (L) [§]	2=moderate	2=moderate	2=moderate	2 = 10-<30%
	3=severe	3=severe	3=severe	3 = 30-<50%
	4=very severe	4=very severe	4=very severe	4 = 50-<70%
				5 = 70-<90%
				6 = 90-100%

[figure not shown]
* Percentage (not score) of body region (not whole body) affected will be entered in the eCRF.

† Neck is assessed as part of the Head (H) body region.

‡ Axillae and groin are assessed as part of the Trunk (T) body region.

§ Buttocks are assessed as part of the Lower limbs (L) body region.

The following definitions are possible efficacy evaluations that can be used in clinical trials in psoriasis ([CHMP/EWP/2454/02, 2004](#)):

- **PASI 90 response:** subjects achieving $\geq 90\%$ improvement (reduction) in PASI score compared to baseline are defined as PASI 90 responders

2.5.3 Definition of IGA mod 2011 score and IGA mod 2011 0 or 1 response

The IGA mod 2011 rating scale for overall psoriatic disease (shown in [Table 2-5](#)) has been developed based on a previous version of the scale used in secukinumab phase II studies, and has been updated in collaboration with health authorities (in particular the FDA). The explanations/descriptions of the points on the scale have been improved to ensure appropriate differentiation between the points. It is recommended that the same evaluator conducts the assessments throughout the study whenever possible.

The IGA mod 2011 used in this study is static, i.e., it refers exclusively to the subject's disease state at the time of the assessments, and does not attempt a comparison with any of the subject's previous disease states, whether at baseline or at a previous visit.

Table 2-5 The IGA mod 2011 rating scale

Score	Short Description	Detailed Description
0	Clear	No signs of psoriasis. Post-inflammatory hyperpigmentation may be present.
1	Almost clear	Normal to pink coloration of lesions; no thickening; no to minimal focal scaling.
2	Mild	Pink to light red coloration; just detectable to mild thickening; predominantly fine scaling.
3	Moderate	Dull bright red, clearly distinguishable erythema; clearly distinguishable to moderate thickening; moderate scaling.
4	Severe	Bright to deep dark red coloration; severe thickening with hard edges; severe / coarse scaling covering almost all or all lesions.

Note: Involvement of nails is not part of the assessment.

Subjects require an IGA mod 2011 score at randomization of 3 or 4 in order to participate in the study. Based on this scale, subjects will be considered as **IGA mod 2011 0 or 1 responder** if they achieve a score of 0 or 1 and improve by at least 2 points on the IGA mod 2011 scale compared to baseline.

2.5.4 Statistical hypothesis, model, and method of analysis

The statistical hypothesis for PASI 90 response at Week 16 is that AIN457 300mg Q2W is not superior to AIN457 300mg Q4W in the proportion of subjects with PASI 90 response at Week 16.

The following hypotheses will be tested:

$$H_I: p_1 - p_0 \leq 0 \text{ versus } H_{A1}: p_1 - p_0 > 0,$$

In other words:

H_I : AIN457 300mg Q2W is not superior to AIN457 300mg Q4W with respect to PASI 90 response at Week 16

The primary analysis method for PASI 90 at Week 16 will be evaluated using logistic regression model with treatment group, baseline body weight and baseline PASI score as explanatory variables (see [Section 5 Appendix](#)). Odds ratios will be computed for comparisons of AIN457 300mg Q2W versus AIN457 300mg Q4W utilizing the logistic regression model fitted. In case of non-convergence, for analyses with multiple imputation, confidence intervals for risk difference and p-values from the t-test for the risk difference comparing to 0 will be provided; for analyses with non-responder imputation, Fisher's exact test will be performed and confidence intervals for risk difference will be provided.

The hypotheses H_I will be tested at level 2.5% (one-sided).

Details in primary analysis is provided in [Section 5.4.1.1](#) and the sensitivity analysis are provided in [Section 2.5.6](#)

2.5.5 Handling of missing values/censoring/discontinuations

Response variables based on PASI score and IGA mod 2011 categories will be imputed with multiple imputation (MI) as primary imputation method for the missing values (refer to [Section 5.4.1.2](#)).

Multiple imputation (MI) is a simulation based approach where missing values are replaced by multiple Bayesian draws from the conditional distribution of missing data given the observed data and covariates, creating multiple completed data sets. These completed data sets can then be analyzed using standard methods. Within this analysis the PASI score or IGA mod 2011 categories will be imputed and response variables will be derived based on the imputed scores. In the multiple imputation analysis the response status will be imputed based on the individual treatment arm information.

2.5.6 Supportive analyses

Primary variable and key secondary variable will be evaluated using logistic regression as described in primary analysis method with modified non-responder (mNRI) imputation as a sensitivity method.

Missing values with respect to response variables based on PASI score and IGA 2011 categories will be imputed with non-response regardless to the reason for missing data (e.g. premature study discontinuation, missed visit, administrative issues). Exceptions for modified non-responder imputation method will apply to the following:

- If a subject dropped out of the study prior to last scheduled visit and being responder consecutively at least for two preceding visits, the subject will be imputed as responder for the last scheduled visit.
- If a subject who was responder at visit x-1 and visit x+1 but has missing data at visit x, then the subject will be imputed as responder for visit x only if visit x-1 or visit x+1 are

scheduled 4 weeks or less from visit x. Otherwise missing data at visit x will be imputed with non-response, except for the missing data at last visit in the treatment period.

2.6 Analysis of the key secondary objective

2.6.1 Secondary endpoint

[figure not shown]
The secondary variable in testing strategy is the IGA mod 2011 0 or 1 response at Week 16 (for superiority comparison of AIN457 300 mg Q2W versus AIN457 Q4W). The IGA mod 2011 0 or 1 response at Week 16 will be analyzed analogously to PASI 90 response at Week 16 (i.e., logistic regression analysis).

The analysis of secondary variable will be based on FAS.

2.6.2 Statistical hypothesis, model, and method of analysis

H₂: AIN457 300mg Q2W is not superior to AIN457 300mg Q4W with respect to IGA mod 2011 0 or 1 response at Week 16

Testing Strategy

The family-wise type-I-error will be set to $\alpha=2.5\%$ (one-sided). The graphical approach of Bretz ([Bretz et al 2009](#)) for sequentially rejective testing procedures is used to illustrate the hierarchical testing strategy.

One-sided p-values will be derived. Each hypothesis is tested sequentially at $\alpha=2.5\%$ (one-sided).

The testing sequence will continue to H₂ at α (one-sided) only if H₁ has been rejected.

2.6.3 Handling of missing values/censoring/discontinuations

See [Section 2.5.5](#).

2.7 Analysis of secondary efficacy objective(s)

No other secondary efficacy objectives were analyzed.

2.7.1 Secondary endpoints

Not applicable.

2.7.2 Statistical hypothesis, model, and method of analysis

Not applicable.

2.7.3 Handling of missing values/censoring/discontinuations

Not applicable.

2.8 Safety analyses

All safety analyses will be based on the safety set. Only those visits which were pre-planned in the protocol will be reported in tables and figures for safety variables.

Treatment groups for safety evaluation

Treatment period 1:

- AIN457 300mg Q2W
- AIN457 300mg Q4W
- Any AIN457 dose (Total)

Entire study period:

- AIN457 300mg Q2W
- AIN457 300mg continuous Q4W [REDACTED]

- Any AIN457 dose (Total)

Safety analyses will be performed on treatment received or actual treatment (See [Section 5.4.2](#), Safety Set).

2.8.1 Adverse events (AEs)

For adverse events and other binary safety variables crude incidence will be derived as described below.

All adverse events are summarized based on treatment emergent only. The definition for “treatment emergent” is as below:

- events started after the first dose of study medication or events present prior to the first dose of study medication but increased in severity based on preferred term
- and started prior to the last dose plus 84 days (inclusive)

All adverse events will be listed with “treatment emergent” flag displayed.

The crude incidence of treatment emergent adverse events will be summarized by primary System Organ Class (SOC) and Preferred Term (PT). Confidence intervals for the crude rate will be derived using the score method including continuity correction ([Newcombe 1998](#)) as described in [Section 5.4.2.1](#).

Adverse events will be summarized by presenting, for each treatment group, the number and percentage of subjects having at least one AE, having an AE in each primary system organ class and having each individual AE (preferred term). Summaries will also be presented for AEs by severity and for study treatment related AEs. If a particular AE ‘severity’ is missing, this variable will be listed as missing and treated as missing in summaries. If a subject reported more than one adverse event with the same preferred term, the adverse event with the greatest severity will be presented. If a subject reported more than one adverse event within the same primary system organ class, the subject will be counted only once with the greatest severity at the system organ class level, where applicable.

Adverse events will also be summarized by standardized or customized MedDRA queries (SMQ or CMQ/NMQ). The MedDRA version used for reporting the adverse events will be described in a footnote.

The most common adverse events reported ($\geq z$ % in any group for each preferred term in the table by SOC and PT or $\geq z$ % in any group for each grouping term table) will be presented in descending frequency according to its incidence in secukinumab group starting from the most common event. Here threshold value z is set to 2 (%) but it may be updated following review of the dry run outputs.

Separate summaries will be provided for deaths, serious adverse events, other significant adverse events leading to discontinuation and adverse events leading to dose adjustment or interruption.

Algorithms for date imputations will be provided in [Section 5](#).

For SAEs occurred during screening a listing will be prepared for all subjects screened including screening failures. The adverse events occurred after the treatment errors in those subjects who received erroneously the wrong treatment at least once, will be listed.

2.8.2 Adverse events of special interest / grouping of AEs

Crude incidence rate for adverse events of special interest will be provided as in [Table 2-6](#).

Table 2-6 AEs of special interest

Special AE interest:	Notes (All levels are displayed)
Inflammatory bowel disease [STANDARD](NMQ) (narrow)	Include Crohns (PT) and Ulcerative colitis (PT) and others
Opportunistic infections [FINGOLIMOD](NMQ)	
Candida infections (HLT)	
Herpes viral infections (HLT)	Both Oral and other are included
Staphylococcal infections (HLT)	
MACE (MI, Stroke, Cardiovascular death) [AIN457](NMQ)	
Malignant or unspecified tumours (SMQ)	Including BCC, SCC in SMQ

Malignant or unspecified tumours (SMQ excl BCC and SCC)
[AIN457](NMQ)
Upper respiratory tract infections (HLT)

Other safety topics of interest, such as risks defined in the Risk Management Plan or topics of interest regarding signal detection or routine analysis are defined in the Program Case Retrieval Sheet that is stored in GPS at the path [REDACTED].

Crude rate of important identified and potential risks from Case Retrieval Sheet will be provided for all (non-serious and serious) cases and for all serious cases.

Risk measures and confidence intervals will be derived according to [Section 5](#).

The version of the Case Retrieval Sheet used for the analyses will be described in a footnote. This includes MedDRA version and Novartis MedDRA Query (NMQ) dictionary date.

Important note: For the evaluation of risks primary and secondary system organ classes of the MedDRA dictionary will be considered.

2.8.3 Deaths

Separate summary and listing will be provided for deaths.

2.8.4 Laboratory data

The summary of laboratory evaluations will be presented for two groups of laboratory tests (hematology and serum chemistry).

Descriptive summary statistics for the change from baseline to each study visit will be presented by laboratory test and treatment group. Change from baseline will only be summarized for subjects with both baseline and post baseline values and will be calculated as:

$$\text{change from baseline} = \text{post baseline value} - \text{baseline value}$$

Only “on-treatment” laboratory data will be summarized (i.e. assessments within last dose plus 84 days). All laboratory data will be listed with “on-treatment” flag displayed. If two measurements are taken on the same date/time/CRF visit then use the average of two assessments.

For laboratory test values below Lower Level of Quantification (LLQ) or above Upper Level of Quantification (ULQ) will be imputed as LLQ or ULQ value, respectively. The numerical part of the reported result will be treated as the actual LLQ or ULQ. These laboratory values will be displayed in listings using the standard unit with the reported sign (“<” or “>”).

In addition, shift tables will be provided for all parameters to compare a subject’s baseline laboratory evaluation relative to the most extreme laboratory test value within a treatment period. For the shift tables, the normal laboratory ranges will be used to evaluate whether a particular laboratory test value is normal, low, or high (including category “high and low”). These summaries will be presented by laboratory test and treatment group. Subjects with abnormal laboratory values will be listed and values outside the normal ranges will be flagged.

The following laboratory parameters will be analyzed with respect to numerical Common Terminology Criteria for Adverse Events (CTCAE) grades, given in [Table 2-7](#): hemoglobin, platelets, white blood cell count, neutrophils, lymphocytes, creatinine, total bilirubin (TBL),

gamma-glutamyl transferase (GGT), alanine aminotransferase (ALT), aspartate aminotransferase (AST), alkaline phosphatase (ALP).

The number and percentage of subjects with CTCAE grade newly occurring or worsening after baseline will be presented. These summaries will be split into hematology and chemistry.

Table 2-7 CTCAE grades for laboratory parameters to be analyzed

CTCAE v4.0 Term	Grade 1	Grade 2	Grade 3	Grade 4
HGB decreased (Anemia)	<LLN – 100 g/L	<100 – 80 g/L	<80 g/L	Life-threatening consequences; urgent intervention
Platelet count Decreased	<LLN – 75.0 x10e9 /L	<75.0 - 50.0 x10e9 /L	<50.0 – 25.0 x10e9 /L	<25.0 x 10e9 /L
White blood cell decreased	<LLN - 3.0 x 10e9 /L	<3.0 - 2.0 x 10e9 /L	<2.0 - 1.0 x 10e9 /L	<1.0 x 10e9 /L
Neutrophil count decreased	<LLN - 1.5 x 10e9 /L	<1.5 - 1.0 x 10e9 /L	<1.0 - 0.5 x 10e9 /L	<0.5 x 10e9 /L
Lymphocyte count decreased	<LLN - 0.8 x 10e9/L	<0.8 - 0.5 x 10e9 /L	<0.5 - 0.2 x 10e9 /L	<0.2 x 10e9 /L
Creatinine increased	>ULN - 1.5 x ULN	>1.5 - 3.0 x ULN	>3.0 - 6.0 x ULN	>6.0 x ULN
TBL increased	>ULN - 1.5 x ULN	>1.5 - 3.0 x ULN	>3.0 - 10.0 x ULN	>10.0 x ULN
GGT increased	>ULN - 2.5 x ULN	>2.5 - 5.0 x ULN	>5.0 - 20.0 x ULN	>20.0 x ULN
ALT increased	>ULN - 3.0 x ULN	>3.0 - 5.0 x ULN	>5.0 - 20.0 x ULN	>20.0 x ULN
AST increased	>ULN - 3.0 x ULN	>3.0 - 5.0 x ULN	>5.0 - 20.0 x ULN	>20.0 x ULN
ALP increased	>ULN - 2.5 x ULN	>2.5 - 5.0 x ULN	>5.0 - 20.0 x ULN	>20.0 x ULN
Amylase increased	>ULN – 1.5 x ULN	> 1.5 -2.0 x ULN	>2.0 – 5.0 x ULN	> 5.0 x ULN
Lipase increased	>ULN – 1.5 x ULN	> 1.5 -2.0 x ULN	>2.0 – 5.0 x ULN	> 5.0 x ULN

Shift tables will be presented comparing baseline laboratory result (CTCAE grade) with the worst results (expressed in CTCAE grade) during the treatment phase analyzed. Of note, baseline will be defined as last assessment prior to first dosing in initial treatment phase. If no pre-treatment value exists, also a value recorded after first dose can be used as baseline if it was collected on the same day as first dose, see [Section 2.1.3](#).

The number and percentage of subjects with newly occurring liver enzyme abnormalities will also be summarized based on the event criteria given in [Table 2-8](#).

Table 2-8 Liver-related events

Parameter	Criterion
ALT	>3xULN; >5xULN; >8xULN; >10xULN, >20xULN
AST	>3xULN; >5xULN; >8xULN; >10xULN; >20xULN
ALT or AST	>3xULN; >5xULN; >8xULN; >10xULN; >20xULN
TBL	>1xULN; >1.5xULN; >2xULN; >3xULN,
ALP	>1.5xULN; >2xULN; >3xULN; >5xULN
ALT or AST & TBL	ALT or AST >3xULN & TBL >1.5xULN; ALT or AST >3xULN & TBL >2xULN; ALT or AST >5xULN & TBL >2xULN; ALT or AST >8xULN & TBL >2xULN; ALT or AST >10xULN & TBL >2xULN; ALT or AST >20xULN & TBL >2xULN;
ALP & TBL	ALP >3xULN & TBL >2xULN ALP >5xULN & TBL >2xULN
ALT or AST & TBL & ALP	ALT or AST >3xULN & TBL >2xULN & ALP <2xULN (Potential Hy's Law) Note: elevated ALP may suggest obstruction as a consequence of gall bladder or bile duct disease; ALP may also be increased in malignancy. FDA therefore terms Hy's Law cases as indicators of pure hepatocellular injury . This does not mean that cases of ALT or AST >3xULN & TBL >2xULN & ALP >2xULN may not result in severe DILI. ALT or AST >3xULN & TBL >2xULN & ALP <2xULN (Potential Hy's Law) or reported Hy's Law case Note: "Hy's Law case" is a lower level term in MedDRA (10070546) and may be reported as AE.

For a combined criterion to be fulfilled, all conditions have to be fulfilled on the same visit. The criteria are not mutually exclusive, e.g., a subject with ALT = 6.42xULN is counted for ALT >3xULN and ALT >5xULN.

Individual subject data listings will be provided for subjects with notably abnormal laboratory values (reference to Protocol Amendment 1, Appendix 1) and newly occurring or worsening abnormal laboratory data by CTC grades. Data of subjects with newly occurring liver enzyme abnormalities will be listed in an additional listing.

Fasting laboratory tests including fasting plasma glucose and fasting lipids will be evaluated only at screening. No analysis will be done for these measurements.

For urinalysis, standard dipstick measurements for specific gravity, protein, glucose, pH, blood, urine blood (non-hemolyzed), urine blood (hemolyzed), bilirubin, ketones, WBC will be done at screening. No analysis will be done for these measurements.

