**Table 6-1 Assessment schedule**

Periods	Screen	Treatment Period 1								Treatment Period 2						Unscheduled visit (a)	Post Treatment Follow-up Period	
		Week (relative to randomization (R))	≥-4 to ≤-1	R	1	2	3	4	8	12	16 EOT1	20	24	28	32		40	52 EOT2
Day	≥-28 to ≤-7	1	8	15	22	29	57	85	113	141	169	197	225	281	365	393	421	
Assessment																		
Site visit	S	S	S	S	S	S	S	S	S	S	S	S	S	S	S	S	S	
Obtain informed consent	X																	
Demographics	X																	
Inclusion/exclusion criteria	X	X																
Smoking history	X																	
Psoriasis medical history / previous psoriasis therapies	X																	
Other medical history and prior medications	X																	
Concomitant medications	X	X	X	X	X	X	X	X	X	X	X	X	X	X	X	X	X	
Physical examination	S	S	S			S			S				S		S	S		
Height	X																	
Weight	X	X							X				X		X	X		
Vital signs (blood pressure and pulse)	X	X	X	X	X	X	X	X	X	X	X	X	X	X	X	X	X	

R= Randomization; X = assessment to be recorded on clinical database; S = assessment to be recorded on source documentation.  
(a) Unscheduled visit: The assessment(s) performed at an unscheduled visit are at the investigator's discretion.

Week (relative to randomization (R))	Screen	Treatment Period 1								Treatment Period 2						Unscheduled visit (a)	Post Treatment Follow-up Period	
		R	1	2	3	4	8	12	16 EOT1	20	24	28	32	40	52 EOT2		F4 56	F8 60
Day	≥-4 to ≤-1	1	8	15	22	29	57	85	113	141	169	197	225	281	365	393	421	
Assessment	≥-28 to ≤-7																	
Laboratory sampling: safety panel (Clinical chemistry, hematology)	X	X		X		X	X	X	X	X	X		X		X	X	X	
Fasting labs: glucose, lipid panel)		X							X		X		X		X			
QuantiFERON® TB-Gold In-tube test	X														X	X		
Serum pregnancy test (WoCBP only)	X																	
Urine pregnancy test (local) (WoCBP only)		S							S				S	S	S	S	S	
Urinalysis (local)	X															X		

TB: tuberculosis; X = assessment to be recorded on clinical database; S = assessment to be recorded on source documentation; WoCBP = women of child bearing potential  
(a) Unscheduled visit: The assessment(s) performed at an unscheduled visit are at the investigator's discretion.

Periods	Screen	Treatment Period 1								Treatment Period 2						Unscheduled visit (a)	Post Treatment Follow-up Period	
Week (relative to randomization (R))	≥-4 to ≤-1	R	1	2	3	4	8	12	16 EOT1	20	24	28	32	40	52 EOT2		F4 56	F8 60
Assessment	Day ≥-28 to ≤-7	1	8	15	22	29	57	85	113	141	169	197	225	281	365	393	421	

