##### **6.5.4.2 Clinical chemistry**

Serum chemistry will include urea, creatinine, total bilirubin, AST (SGOT), ALT (SGPT), Gamma-Glutamyl Transferase (GGT), alkaline phosphatase, sodium, potassium, bicarbonate, calcium, phosphorous, total protein, albumin, amylase, lipase and uric acid. Serum chemistry will be measured at all scheduled study visits within the visit window specified in [Table 6-1](#).

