##### **6.5.4.3 Fasting Laboratory evaluations**

Fasting (8 hour duration with water *ad libitum*) laboratory evaluations will be assessed as at baseline as indicated in [Table 6-1](#).

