###### **6.5.4.3.1 Plasma glucose**

Fasting plasma glucose will be taken as a fasting blood sample as indicated in [Table 6-1](#).

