###### **6.5.4.3.2 Lipid panel**

A lipid profile including High Density Lipoprotein (HDL), Low Density Lipoprotein (LDL), cholesterol, triglycerides, lipoprotein (a), apolipoprotein B, apolipoprotein A-1, and adiponectin will be measured from a fasting blood sample as indicated in [Table 6-1](#).

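### SAP 2.8.4 places fasting glucose and lipids at screening only and drops them from analysis, but Protocol Table 6-1 collects them at baseline and at four post-baseline visits

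*SAP*

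**What the plan says.** SAP 2.8.4 (Laboratory data) says of the fasting tests: "Fasting laboratory tests including fasting plasma glucose and fasting lipids will be evaluated only at screening. No analysis will be done for these measurements". The paragraph after it treats urinalysis the same way: done at screening, not analysed. The summaries planned in that section cover two groups, hematology and serum chemistry.

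Protocol Table 6-1 has a row "Fasting labs: glucose, lipid panel" with marks at Randomization and Weeks 16, 24, 32 and 52 and none in the screening column. The table's key reads "X = assessment to be recorded on clinical database", so these results go into the database.

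The protocol text leaves the timing to that table. Section 6.5.4.3 says fasting "laboratory evaluations will be assessed as at baseline as indicated in" Table 6-1. Section 6.5.4.3.1 says "Fasting plasma glucose will be taken as a fasting blood sample as indicated in" the same table. Section 6.5.4.3.2 defines the panel: "A lipid profile including High Density Lipoprotein (HDL), Low Density Lipoprotein (LDL), cholesterol, triglycerides, lipoprotein (a), apolipoprotein B, apolipoprotein A-1, and adiponectin", again timed by the table.

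Protocol 9.5.2 names three laboratory groups for summary (hematology, serum chemistry, urinalysis) and then provides shift tables for all laboratory parameters. Protocol Table 2-1 makes clinical laboratory variables, up to 52 weeks, part of the secondary safety endpoint.

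**The concern.** Read together, the two SAP sentences give a reason and a consequence: the tests are done once before treatment, so there is nothing to analyse. If the tests are in fact repeated on treatment, the reason fails, and data gathered to compare the regimens go unsummarised.

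What is at stake is a group-level safety signal. A drift in fasting glucose or lipids over the year, or more subjects leaving the normal range under one regimen, would appear in no by-arm table. The trial compares a higher-exposure regimen with the approved one in subjects of at least 90 kg. The SAP lists major adverse cardiovascular events among its events of special interest, so metabolic laboratory data are a natural complement.

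**Working it through.** The plan gives no figure to reproduce. The check is a reading of the schedule, followed by a count of what is left out.

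**1. When the samples are taken.** Table 6-1 has 18 columns: Screen, R, Weeks 1, 2, 3, 4, 8, 12, 16, 20, 24, 28, 32, 40, 52, Unscheduled, F4 and F8. Splitting the rows cell by cell gives:

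| Row | Cells | Mark at Screen? | Marks at scheduled visits up to Week 52 |
|---|---|---|---|
| Fasting glucose and lipids | 18 | No | R, 16, 24, 32, 52 |
| Safety panel | 18 | Yes | Screen, R, 2, 4, 8, 12, 16, 20, 24, 32, 52 |
| Serum pregnancy test | 18 | Yes | Screen |
| Urinalysis | 18 | Yes | Screen |

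A shifted column does not explain the empty screening cell. The neighbouring rows have the same number of cells and do carry a screening mark. The urinalysis row agrees with what the SAP says about urinalysis. All five fasting visits also carry a safety-panel sample. The layout is uncertain only around the Unscheduled, F4 and F8 columns, which does not affect this row.

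Result: 0 collections at screening, 1 at baseline, 4 after baseline.

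**2. Whether another summary covers them.** The fasting analytes are glucose (1) plus HDL, LDL, cholesterol, triglycerides, lipoprotein (a), apolipoprotein B, apolipoprotein A-1 and adiponectin (8), which makes 9.

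- Protocol 6.5.4.2 ("Serum chemistry will include urea, creatinine, total bilirubin" and so on) lists 17 analytes; overlap 0.
- SAP Table 2-7 (CTCAE grades) has 13 terms; overlap 0.
- Protocol Appendix 1 (notable values) has 4 liver + 6 hematology = 10 variables; overlap 0.
- SAP Table 2-8 covers liver parameters only; overlap 0.

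The SAP's general sentence on shift tables for all parameters does not rescue these tests, because the later sentence excluding them from analysis is specific to them.

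**3. How much output is missing.**

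- Change from baseline by visit: 4 visits × 9 analytes = 36 summaries per treatment group; 0 planned.
- Normal-range shifts: 9 per treatment group and analysis period; 0 planned.
- Collections: at most 4 × 165 = 660 per arm with full attendance. This is an upper bound, since no dropout rate is given.

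**4. Whether the data would qualify as on-treatment.** SAP 2.1.5 sets the limit at last dose plus 84 days. The last planned dose is at Week 48, which is Day 48 × 7 + 1 = 337, and 337 + 84 = Day 421. The Week 52 sample is scheduled on Day 365, so all four collections qualify for subjects who complete dosing.

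**5. Which visit windows apply.** Combining the windows of SAP Table 2-1 under the rule in SAP 2.4.2 for parameters not measured at every visit:

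| Fasting visit | Windows combined | Days |
|---|---|---|
| Week 16 | Weeks 1 to 16 | 2–127 |
| Week 24 | Weeks 20 and 24 | 128–183 |
| Week 32 | Weeks 28 and 32 | 184–253 |
| Week 52 | Weeks 40 and 52, upper limit extended | 254–435 |

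**The case against.** The strongest reply is that only a wrong sentence about timing has been shown. Neither Protocol 9.5.2 nor SAP 2.8.4 names fasting tests among the groups to be summarised. The protocol's phrase about shift tables for all parameters follows the three-group sentence and may be limited to it. The endpoint wording does not require every collected analyte to be tabulated, and the SAP is open about not analysing these. This stands in part: there is no clear breach of a planned fasting-test analysis. The omission still lacks support, because the only visible reason for it is a schedule that Table 6-1 contradicts. SAP Section 4, on changes to protocol-specified analyses, shows no entry in the text supplied.

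Second, Protocol 6.5.4.3 is loosely worded and can be read as baseline only, and the SAP may use screening loosely for the pre-treatment period. That could account for the Randomization sample. It cannot account for Weeks 16, 24, 32 and 52, and the glucose and lipid subsections both defer to the table.

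Third, the SAP cites Protocol Amendment 1, and the version of the supplied protocol cannot be confirmed from its text. Parts of both documents are also blacked out. A version difference is possible, so the mismatch is between the documents as supplied. Coverage in hidden text is unlikely given the explicit statement that no analysis will be done.

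Fourth, the stakes are modest. All laboratory data are listed, out-of-range values are flagged, and clinically significant values can be reported as adverse events, which are summarised by arm. This is correct, and it is why the point does not threaten the trial's main conclusions. Listings and individual events do not, however, show a shift in a group's distribution.

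**Conclusion.** The point holds. SAP 2.8.4 misstates when fasting glucose and lipids are collected, and as written it leaves all four post-baseline collections of nine analytes without a by-arm summary. The count of 36 change summaries per treatment group measures missing output. It does not measure harm, bias or loss of power.

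The conclusion rests on Table 6-1 being the operative schedule, on the two supplied documents being meant to work together, and on no fasting-test summary lying in redacted text. Efficacy analyses and error control are untouched. It should be corrected because the data bear on the stated 52-week safety comparison and the correction is easy.

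**What to change.** In SAP 2.8.4, replace the two sentences on fasting tests with the Table 6-1 schedule: Randomization and Weeks 16, 24, 32 and 52. Reword Protocol 6.5.4.3 so that it plainly agrees with the table.

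Then add fasting glucose and the eight lipid-panel analytes to:

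- the descriptive on-treatment change-from-baseline summaries at Weeks 16, 24, 32 and 52, by the SAP 2.8 safety treatment groups and with the combined windows derived above;
- the normal-range shift tables, comparing baseline with the most extreme value in each treatment period, not visit by visit.

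No test or confidence interval is needed, in keeping with the other laboratory tables. If the sponsor decides against summarising these tests, the timing statement still has to be corrected, and the omission should be recorded with its reason in SAP Section 4.

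The cost is one SAP paragraph, one protocol sentence and a few standard descriptive tables. No new samples, visits or methods are involved.
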